##### **7.1.1.4.2 Concomitant Medications**

The investigator or qualified designee will record medication, if any, taken by the subject during the trial. All medications related to reportable SAEs and ECIs should be recorded as defined in Section 7.2.

#### **7.1.1.5 Disease Details and Treatments**

##### **7.1.1.5.1 Disease Details**

The investigator or qualified designee will obtain prior and current details regarding disease status.

##### **7.1.1.5.2 Prior Treatment Details**

The investigator or qualified designee will review all prior cancer treatments including systemic treatments, radiation and surgeries.

##### **7.1.1.5.3 Subsequent Anti-Cancer Therapy Status**

The investigator or qualified designee will review all new anti-neoplastic therapy initiated after the last dose of trial treatment. If a subject initiates a new anti-cancer therapy within 30 days after the last dose of trial treatment, the 30 day Safety Follow-up visit must occur before the first dose of the new therapy. Once new anti-cancer therapy has been initiated the subject will move into survival follow-up.

#### **7.1.1.6 Assignment of Screening Number**

Each subject will be assigned only one screening number. Screening numbers must not be re-used for different subjects. Any subject who is screened multiple times will retain the original screening number assigned at the initial screening visit.

#### **7.1.1.7 Assignment of Randomization Number**

Once an allocation number is assigned to a subject, it can never be re-assigned to another subject. A single subject cannot be assigned more than 1 allocation number. Note: although this is described as a “randomization number,” this study is not randomized.

#### **7.1.1.8 Trial Compliance (Medication/Diet/Activity/Other)**

Interruptions from the protocol specified treatment plan for greater than 18 weeks between pembrolizumab doses due to toxicity will require written documentation on subject management.

### **7.1.2 Clinical Procedures/Assessments**

#### **7.1.2.1 Adverse Event (AE) Monitoring**

The investigator or qualified designee will assess each subject to evaluate for potential new or worsening AEs as specified in the Trial Flow Chart and more frequently if clinically indicated. Adverse experiences will be graded and recorded throughout the study and during the follow-up period according to NCI CTCAE Version 4.0 (see Section 11.2). Toxicities will be characterized in terms regarding seriousness, causality, toxicity grading, and action taken with regard to trial treatment.

Please refer to section 7.2 for detailed information regarding the assessment and recording of AEs.

#### **7.1.2.2 Full Physical Exam**

The investigator or qualified designee will perform a complete physical exam during the screening period. Clinically significant abnormal findings should be recorded as medical history.

#### **7.1.2.3 Directed Physical Exam**

For cycles that do not require a full physical exam per the Trial Flow Chart, the investigator or qualified designee will perform a directed physical exam as clinically indicated prior to trial treatment administration.

#### **7.1.2.4 Vital Signs**

The investigator or qualified designee will take vital signs at screening, prior to the administration of each dose of trial treatment and at treatment discontinuation as specified in the Trial Flow Chart (Section 6.0). Vital signs should include temperature, pulse, respiratory rate, weight and blood pressure. Height will be measured at screening only.

#### **7.1.2.5 Eastern Cooperative Oncology Group (ECOG) Performance Scale**

The investigator or qualified designee will assess ECOG status (see Section 11.1) at screening, prior to the administration of each dose of trial treatment and discontinuation of trial treatment as specified in the Trial Flow Chart.

#### **7.1.2.6 12-Lead ECG**

A standard 12-lead ECG will be performed using local standard procedures once at screening. Clinically significant abnormal findings should be recorded as medical history.

#### **7.1.2.7 Tumor Imaging and Assessment of Disease**

Subjects will be evaluated every 9 weeks (63 +/- 7 days) with radiographic imaging to assess response to treatment. All imaging obtained on study will be assessed using a modified Response Evaluation Criteria in Solid Tumors (RECIST) 1.1 for determination of objective response rate (ORR) and progression-free survival (PFS). Subjects will continue with the assigned study treatment until RECIST 1.1-defined progression of disease, unacceptable toxicity, intercurrent illness that prevents further administration of treatment, investigator's decision to withdraw the subject, subject withdraws consent, pregnancy of the subject, noncompliance with trial treatment or procedure requirements, administrative reasons, or the subject has received 35 trial treatments of pembrolizumab. Treatment may continue despite RECIST 1.1 defined progression if the subject is clinically stable and is considered to be deriving clinical benefit by the investigator. For further information, see Appendix Section 13.3.

#### **7.1.2.8 Brain Imaging**

For patients who have prior history of brain metastases, screening brain imaging will need to be obtained. MRI is the preferred imaging modality.

#### **7.1.2.9 Tumor Tissue Collection and Correlative Studies Blood Sampling**

For the first three cycles, prior to treatment, 100 mL of additional blood/serum will be collected for correlative research studies. These samples may be collected up to three days prior to treatment. An additional sample of 100mL of blood/serum will also be collected at the time of progression. All blood drawn must begin processing a maximum of two hours after being drawn. Samples from patients at sites close enough to UCLA to allow blood processing within two hours will be couriered for processing. Sites that are not near enough to allow blood processing within two hours at UCLA will process the correlative blood samples themselves. Sample collection, and storage instructions for serum samples will be provided in the lab manual.

#### **7.1.3 Laboratory Procedures/Assessments**

Details regarding specific laboratory procedures/assessments to be performed in this trial are provided below. Laboratory Safety Evaluations (Hematology, Chemistry and Urinalysis)

**Product:** Pembrolizumab  
**Protocol/Amendment No.:**

35

Laboratory tests for hematology, chemistry, urinalysis, and others are specified in Table 5.

Table 5 Laboratory Tests

Hematology	Chemistry	Urinalysis	Other
Hematocrit	Albumin	Blood	Serum $\beta$ -human chorionic gonadotropin†
Hemoglobin	Alkaline phosphatase	Glucose	( $\beta$ -hCG)†
Platelet count	Alanine aminotransferase (ALT)	Protein	PT (INR)
WBC (total and differential)	Aspartate aminotransferase (AST)	Specific gravity	aPTT
Red Blood Cell Count	Lactate dehydrogenase (LDH)	Microscopic exam ( If abnormal )	Total triiodothyronine (T3)
Absolute Neutrophil Count	Carbon Dioxide ‡	results are noted	Free thyroxine (T4)
Absolute Lymphocyte Count	( CO2 or bicarbonate )	Urine pregnancy test †	Thyroid stimulating hormone (TSH)
	Uric Acid		
	Calcium		
	Chloride		Blood for correlative studies
	Glucose		
	Phosphorus		
	Potassium		
	Sodium		
	Magnesium		
	Total Bilirubin		
	Direct Bilirubin ( If total bilirubin is elevated above the upper limit of normal )		
	Total protein		
	Blood Urea Nitrogen		

Hematology	Chemistry	Urinalysis	Other

† Perform on women of childbearing potential only. If urine pregnancy results cannot be confirmed as negative, a serum pregnancy test will be required.
 
‡ If considered standard of care in your region.
			

Laboratory tests for screening or entry into the Second Course Phase should be performed within 10 days prior to the first dose of treatment. After Cycle 1, pre-dose laboratory procedures can be conducted up to 72 hours prior to dosing. Results from the C1D1 tests and C1D1 of Second Course Phase are for information only and do not need to be checked prior to therapy. Other results must be reviewed by the investigator or qualified designee and found to be acceptable prior to each dose of trial treatment.

#### **7.1.4 Other Procedures**

##### **7.1.4.1 Withdrawal/Discontinuation**

When a subject discontinues/withdraws prior to trial completion, all applicable activities scheduled for the final trial visit should be performed at the time of discontinuation. Any adverse events which are present at the time of discontinuation/withdrawal should be followed in accordance with the safety requirements outlined in Section 7.2 - Assessing and Recording Adverse Events. Subjects who a) attain a CR or b) complete 24 months of treatment with pembrolizumab may discontinue treatment with the option of restarting treatment if they meet the criteria specified in Section 7.1.5.5. After discontinuing treatment following assessment of CR, these subjects should return to the site for a Safety Follow-up Visit (described in Section 7.1.5.3.1) and then proceed to the Follow-Up Period of the study (described in Section 7.1.5.4).

##### **7.1.4.2 Blinding/Unblinding**

#### **7.1.5 Visit Requirements**

Visit requirements are outlined in Section 6.0 - Trial Flow Chart. Specific procedure-related details are provided above in Section 7.1 - Trial Procedures.

##### **7.1.5.1 Screening**

###### **7.1.5.1.1 Screening Period**

Approximately 28 days prior to start of treatment, potential subjects will be evaluated to determine that they fulfill the entry requirements. Screening procedures may be repeated after consultation with the UCLA DSMB.

Written consent must be obtained prior to performing any protocol specific procedure. Results of a test performed prior to the subject signing consent as part of routine clinical management are acceptable in lieu of a screening test if performed within the specified time frame. Screening procedures are to be completed within 28 days prior to the first dose of trial treatment except for the following:

- Laboratory tests are to be performed within 10 days prior to the first dose of trial treatment.
- For women of reproductive potential, a urine pregnancy test will be performed within 72 hours prior to first dose of trial treatment. If urine pregnancy results cannot be confirmed as negative, a serum pregnancy test, performed by the local study site laboratory, will be required.
- Tumor imaging must be performed within 30 days prior to the first dose of trial treatment.

Subjects may be rescreened after initially failing to meet the inclusion/exclusion criteria. Results from assessments performed during the initial screening period are acceptable in lieu of a repeating a screening test if performed within the specified time frame and the results meet the inclusion/exclusion criteria.

#### **7.1.5.2 Treatment Period**

Visit requirements are outlined in Section 6.0 - Trial Flow Chart.

#### **7.1.5.3 Post-Treatment Visits**

The discontinuation visit should be conducted approximately within 28 +/- 7 days after the last dose of trial treatment or before the initiation of a new antineoplastic treatment, whichever comes first.

#### **7.1.5.4 Follow-up Visits**

Subjects who discontinue trial treatment for a reason other than disease progression will move into the Follow-up Phase and should continue to be assessed every 9 weeks ( $63 \pm 7$  days) by radiologic imaging to monitor disease status. Follow-up Visit 1 should be scheduled 3 months after the last dose of trial treatment. Assessment for drug-related immune-related adverse events should occur at Follow-up Visit 1. Follow-up Visit 2 should occur 6 months after the last dose of trial treatment. After Follow-up Visit 2 subjects should continue to be assessed every 9 weeks ( $63 \pm 7$  days) by radiologic imaging to monitor disease status and initiation of new antineoplastic therapy. Unless otherwise noted in the flow chart, every effort should be made to collect subject information on the start of new tyrosine kinase inhibitor therapy in patients harboring EGFR-sensitizing mutations, disease progression, and death.

##### **7.1.5.4.1 Survival Follow-up**

Once a subject completes the follow-up visits, the subject moves into the survival follow-up phase and should come in for a visit (approximately every 2 months) for survival status and to receive scans until death, withdrawal of consent, or the end of the study, whichever occurs first. It is recognized that based on variability of post-study management, the frequency of this visit is anticipated to vary significantly. In patients for whom follow up is less frequent than every 3 months, we will call patients to evaluation vital status, and whether they are currently on an EGFR-TKI.

#### **7.1.5.5 Second Course Phase**

Subjects may be eligible for up to one year of additional treatment with pembrolizumab via the Second Course Phase if the treating investigator believes that the patient will benefit from the Second Course Phase. Patients will not need to be re-registered or re-screened in order to participate.

## **7.2 Assessing and Recording Adverse Events**

An adverse event is defined as any untoward medical occurrence in a patient or clinical investigation subject administered a pharmaceutical product and which does not necessarily have to have a causal

relationship with this treatment. An adverse event can therefore be any unfavorable and unintended sign (including an abnormal laboratory finding, for example), symptom, or disease temporally associated with the use of a medicinal product or protocol-specified procedure, whether or not considered related to the medicinal product or protocol-specified procedure. Any worsening (i.e., any clinically significant adverse change in frequency and/or intensity) of a preexisting condition that is temporally associated with the use of the Merck's product, is also an adverse event.

Changes resulting from normal growth and development that do not vary significantly in frequency or severity from expected levels are not to be considered adverse events. Examples of this may include, but are not limited to, teething, typical crying in infants and children and onset of menses or menopause occurring at a physiologically appropriate time.

Merck product includes any pharmaceutical product, biological product, device, diagnostic agent or protocol-specified procedure, whether investigational (including placebo or active comparator medication) or marketed, manufactured by, licensed by, provided by or distributed by Merck for human use.

Adverse events may occur during the course of the use of Merck product in clinical trials or as prescribed in clinical practice, from overdose (whether accidental or intentional), from abuse, and from withdrawal.

All adverse events that occur after the consent form is signed but before treatment allocation/randomization must be reported by the investigator if they cause the subject to be excluded from the trial, or are the result of a protocol-specified intervention, including but not limited to washout or discontinuation of usual therapy, diet, placebo treatment or a procedure.

Progression of the cancer under study is not considered an adverse event unless it is considered to be drug related by the investigator.

From the time of treatment allocation/randomization through 30 days following cessation of treatment, all adverse events must be reported by the investigator. Such events will be recorded at each examination on the Adverse Event case report forms/worksheets. The reporting timeframe for adverse events meeting any serious criteria is described in section 7.2.3.1. The investigator will make every attempt to follow all subjects with non-serious adverse events for outcome.

Adverse events will not be collected for subjects during the pre-screening period (for determination of archival tissue status) as long as that subject has not undergone any protocol-specified procedure or intervention. If the subject requires a blood draw, fresh tumor biopsy etc., the subject is first required to provide consent to the main study and AEs will be captured according to guidelines for standard AE reporting.

All adverse events will be recorded from the time the consent form is signed through 30 days following cessation of treatment and at each examination on the Adverse Event case report forms/worksheets. The reporting timeframe for adverse events meeting any serious criteria is described in section 7.2.3.1.

### **7.2.1 Definition of an Overdose for This Protocol and Reporting of Overdose to the UCLA DSMB and to Merck**

For purposes of this trial, an overdose of pembrolizumab will be defined as any dose of 1,000 mg or greater ( $\geq 5$  times the indicated dose). No specific information is available on the treatment of overdose of pembrolizumab. Appropriate supportive treatment should be provided if clinically indicated. In the event of overdose, the subject should be observed closely for signs of toxicity. Appropriate supportive treatment should be provided if clinically indicated.

If an adverse event(s) is associated with (“results from”) the overdose of a Merck product, the adverse event(s) is reported as a serious adverse event, even if no other seriousness criteria are met.

If a dose of Merck’s product meeting the protocol definition of overdose is taken without any associated clinical symptoms or abnormal laboratory results, the overdose is reported as a non-serious Event of Clinical Interest (ECI), using the terminology “accidental or intentional overdose without adverse effect.”

All reports of overdose with and without an adverse event must be reported within 24 hours to the UCLA DSMB and within 2 working days hours to Merck Global Safety. (Attn: Worldwide Product Safety; [contact])

### **7.2.2 Reporting of Pregnancy and Lactation to UCLA DSMB and to Merck**

Although pregnancy and lactation are not considered adverse events, it is the responsibility of investigators or their designees to report any pregnancy or lactation in a subject (spontaneously reported to them), that occurs during the trial.

Pregnancies and lactations that occur after the consent form is signed but before treatment allocation/randomization must be reported by the investigator if they cause the subject to be excluded from the trial, or are the result of a protocol-specified intervention, including but not limited to washout or discontinuation of usual therapy, diet, placebo treatment or a procedure.

Pregnancies and lactations that occur from the time of treatment allocation/randomization through 120 days following cessation of Sponsor’s product, or 30 days following cessation of treatment if the subject initiates new anticancer therapy, whichever is earlier, must be reported by the investigator. All reported pregnancies must be followed to the completion/termination of the pregnancy. Pregnancy outcomes of spontaneous abortion, missed abortion, benign hydatidiform mole, blighted ovum, fetal death, intrauterine death, miscarriage and stillbirth must be reported as serious events (Important Medical Events). If the pregnancy continues to term, the outcome (health of infant) must also be reported.

Such events must be reported within 24 hours to the UCLA DSMB and within 2 working days to Merck Global Safety. (Attn: Worldwide Product Safety; [contact])

### **7.2.3 Immediate Reporting of Adverse Events to UCLA DSMB and Merck**

#### **7.2.3.1 Serious Adverse Events**

A serious adverse event is any adverse event occurring at any dose or during any use of Merck's product that:

- Results in death;
- Is life threatening;
- Results in persistent or significant disability/incapacity;
- Results in or prolongs an existing inpatient hospitalization;
- Is a congenital anomaly/birth defect;
- Is a new cancer (that is not a condition of the study);
- Is associated with an overdose;
- Is another important medical event

Refer to Table 6 for additional details regarding each of the above criteria.

Any serious adverse event, or follow up to a serious adverse event, including death due to any cause other than progression of the cancer under study that occurs to any subject from the time the consent is signed through 90 days following cessation of treatment, or the initiation of new anti-cancer therapy, whichever is earlier, whether or not related to Merck product, must be reported to UCLA DSMB.

Additionally, any serious adverse event, considered by an investigator who is a qualified physician to be related to Merck product that is brought to the attention of the investigator at any time outside of the time period specified in the previous paragraph also must be reported immediately to the UCLA DSMB.

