The End of Treatment and Follow-up visit procedures are listed in Section 6 (Protocol Flow Chart) and Section 7.1.5 (Visit Requirements). After the end of treatment, each subject will be followed for 30 days for adverse event monitoring (serious adverse events will be collected for 90 days after the end of treatment as described in Section 7.2.3.1). Subjects who discontinue for reasons other than progressive disease will have post-treatment follow-up for disease status until disease progression, initiating a non-study cancer treatment, withdrawing consent or becoming lost to follow-up. After documented disease progression each subject will be followed by telephone for overall survival until death, withdrawal of consent, or the end of the study, whichever occurs first.

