#### **7.2.3.2 Events of Clinical Interest**

Selected non-serious and serious adverse events are also known as Events of Clinical Interest (ECI) and must be reported within 24 hours to the UCLA DSMB and within 2 working days to Merck Global Safety. (Attn: Worldwide Product Safety; [contact]).

For the time period beginning when the consent form is signed until treatment allocation/randomization, any ECI, or follow up to an EVI, that occurs to any subject must be reported within 24 hours to the Sponsor and within 2 working days to Merck Global Safety if it causes the subject to be excluded from the trial, or is the result of a protocol-specified intervention, including but not limited to washout or discontinuation of usual therapy, diet, placebo treatment or a procedure.

For the time period beginning at treatment allocation/randomization through 90 days following cessation of treatment, or 30 days following cessation of treatment if the subject initiates new anticancer therapy, whichever is earlier, any ECI, or follow up to an ECI, whether or not related to Merck product, must be reported within 24 hours to the Sponsor and within 24 hours to Merck Global Safety.

. Events of clinical interest for this trial include:

1. An overdose of Merck product, as defined in Section 7.2.1 - Definition of an Overdose for This Protocol and Reporting of Overdose, that is not associated with clinical symptoms or abnormal laboratory results.
2. An elevated AST or ALT lab value that is greater than or equal to 3X the upper limit of normal and an elevated total bilirubin lab value that is greater than or equal to 2X the upper limit of normal and, at the same time, an alkaline phosphatase lab value that is less than 2X the upper limit of normal, as determined by way of protocol-specified laboratory testing or unscheduled laboratory testing.\*

\*Note: These criteria are based upon available regulatory guidance documents. The purpose of the criteria is to specify a threshold of abnormal hepatic tests that may require an additional evaluation for an underlying etiology

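### All-cause SAE reporting stops when new anti-cancer therapy starts, with no 30-day minimum, so after an early TKI start it closes before the AE, ECI and pregnancy windows

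*Combined protocol and SAP*

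**What the plan says.** All places are in the combined protocol and SAP.

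- **SAEs (7.2.3.1).** Any SAE, whatever its cause, is reported to the DSMB from consent "through 90 days following cessation of treatment, or the initiation of new anti-cancer therapy, whichever is earlier". Death from progression is excepted. After that point the duty continues only for "any serious adverse event, considered by an investigator who is a qualified physician to be related to Merck product", with no time limit.
- **AEs (7.2).** The duty runs "through 30 days following cessation of treatment, all adverse events must be reported by the investigator". New therapy does not shorten it. For serious events, 7.2 refers the reporting timeframe to 7.2.3.1.
- **ECIs (7.2.3.2).** The window is 90 days, or "30 days following cessation of treatment if the subject initiates new anticancer therapy, whichever is earlier, any ECI".
- **Pregnancy and lactation (7.2.2).** The window is 120 days, "or 30 days following cessation of treatment if the subject initiates new anticancer therapy, whichever is earlier, must be reported by the investigator".
- **Discontinuation (5.6).** "serious adverse events will be collected for 90 days after the end of treatment as described in Section 7.2.3.1". The cut-off at new therapy is not mentioned, but the sentence defers to 7.2.3.1.
- **New therapy (7.1.1.5.3).** "If a subject initiates a new anti-cancer therapy within 30 days after the last dose of trial treatment", then "the 30 day Safety Follow-up visit must occur before the first dose of the new therapy", and the subject moves to survival follow-up.
- **DSMB oversight (8.1).** All SAEs go to the DSMB irrespective of attribution, but no post-treatment window is given.

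**The concern.** ECIs and pregnancies have a 30-day floor when new therapy starts, and the AE window is fixed at 30 days. SAEs have no floor. When a TKI begins before day 30, the most serious class of event therefore has the shortest all-cause window. The early safety visit does not help, because it takes place before the new drug is given.

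From the first TKI dose, a report under 7.2.3.1 depends on the investigator linking the event to pembrolizumab. Section 5.2.1.2 expects immune-mediated events up to several months after the last dose. The causality guide in Table 6 asks whether another drug could explain the event, and a newly started TKI is such a drug. An event attributed to it would not need an SAE report to the DSMB. Pembrolizumab followed by a TKI is the sequence the trial sets out to evaluate (4.2.1), so the case is not remote.

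**Working it through.** The plan gives no figure to reproduce. The check compares the closing days of four windows.

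**Inputs.** t is the day new therapy starts, counted from the end of pembrolizumab. I take cessation of treatment and the last dose as the same day. Limits: SAE 90 or t (7.2.3.1); AE 30 (7.2); ECI 90, or 30 with new therapy (7.2.3.2); pregnancy 120, or 30 with new therapy (7.2.2).

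**Formulas, when new therapy starts**
- SAE end = min(90, t)
- AE end = 30; ECI end = min(90, 30) = 30; pregnancy end = min(120, 30) = 30
- Shortfall = max(0, 30 − t)
- SAE end with a 30-day floor = min(90, max(30, t))
- SAE end if the ECI clause were copied = min(90, 30) = 30

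| t | SAE now | AE / ECI / pregnancy | Shortfall | With floor | ECI clause copied |
|---|---|---|---|---|---|
| 7 | 7 | 30 / 30 / 30 | 23 | 30 | 30 |
| 14 | 14 | 30 / 30 / 30 | 16 | 30 | 30 |
| 21 | 21 | 30 / 30 / 30 | 9 | 30 | 30 |
| 29 | 29 | 30 / 30 / 30 | 1 | 30 | 30 |
| 30 | 30 | 30 / 30 / 30 | 0 | 30 | 30 |
| 45 | 45 | 30 / 30 / 30 | 0 | 45 | 30 |
| 60 | 60 | 30 / 30 / 30 | 0 | 60 | 30 |
| no new therapy | 90 | 30 / 90 / 120 | – | 90 | 90 |

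The SAE window is the shortest of the four for every t below 30, and for no t of 30 or more. The floor removes the shortfall and shortens nothing. Copying the ECI clause would also remove it, but would cost 45 − 30 = 15 days at t = 45 and 60 − 30 = 30 days at t = 60.

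**Which t is plausible?** The documents do not say. Dosing is every 21 days and imaging every 63, so a scan due at the cycle 4 visit falls nominally 63 − 42 = 21 days after the cycle 3 dose. If dosing is on schedule, cycle 4 is withheld and the TKI starts at once, t is about 21 and the shortfall is 9 days. Any delay in starting the TKI reduces it, to nothing from day 30.

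**What is missing in those days?** Section 7.2 has all AEs recorded to day 30. It refers the reporting timeframe for serious events elsewhere, but does not exempt them from recording. Section 7.2.4 has every AE assessed for seriousness. The record should therefore exist. What is absent is the immediate report that feeds the DSMB's monthly SAE review (8.1). The DSMB would otherwise depend on the cumulative AE reports (8.1) and a summary report about every six months (8.2.1).

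**The case against.** The best defence is that closing the window at new therapy is a coherent choice. The safety visit is placed before the new drug, the subject then enters survival follow-up, and events caused by the TKI serve no stated objective: for the TKI, 3.2 lists only ORR, PFS and OS. SAEs judged related remain reportable indefinitely. The causality test is a reasonable possibility, and Table 6 does not require every criterion to be met. ECIs, including the liver-test combination, are reportable to day 30 whatever their cause. Section 8.1 asks for all SAEs.

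Most of this stands and limits the size of the point. It does not explain why ECIs and pregnancies have a 30-day floor and SAEs do not. Section 8.1 does not resolve the matter, because it sets no window.

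A reader might infer three stronger things that the documents do not support:

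- **Serious events after an early TKI start are lost to the safety data.** Sections 7.2 and 7.2.4 point the other way up to day 30, and the safety objective in 3.2 rests on tabulated AEs.
- **Patients lose most of a promised 90 days**, for example 90 − 21 = 69 days at t = 21. Section 5.6 states its 90 days by reference to 7.2.3.1, so it makes no separate promise.
- **All-cause reporting must run the full 90 days.** The ECI and pregnancy windows also close at day 30 when new therapy starts, so they support a 30-day floor and nothing longer.

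**Conclusion.** The point holds as a minor gap. For a TKI start on day t below 30, SAEs judged unrelated to pembrolizumab leave immediate DSMB reporting 30 − t days before the AE, ECI and pregnancy windows close. From day 30 onward there is no inversion. The consequence is slower DSMB sight of SAEs attributed to the TKI, when a late immune event and a TKI event are hardest to tell apart.

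This rests on reading 7.2.3.1 as the governing text, as 5.6 and 7.2 both direct, and on counting all windows from the same day. The distribution of t is unknown and no event rate is assumed, so the number of SAEs affected among about 25 patients cannot be stated. The ORR analysis and the AE tabulation are not invalidated.

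**What to change.** In 7.2.3.1, require all SAEs, regardless of attribution, to be reported through 90 days after cessation or, if new anti-cancer therapy starts earlier, through the later of day 30 and the start of that therapy. In days this is min(90, max(30, t)). Leave the open-ended duty for related SAEs unchanged. Reword 5.6 to state the same rule. Do not reuse the ECI wording, for the reason shown in the table.

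The cost is one clause and one conforming edit. No visit is added: AE recording to day 30 already requires the site to learn of these events. The downside is a few extra SAE reports before day 30, some confounded by the TKI. Keeping the full 90 days whatever therapy follows is an optional extension. It would mean more confounded reports and is not needed to remove the inversion.
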